Bacterial sepsis is characterized by an early phase of pro-inflammatory “cytokine storm”. It is now recognized that this is followed by a phase characterized by monocyte deactivation, impaired neutrophil function, lymphocyte dysfunction and apoptosis [51, 52], increased production of IL-10 and TGF- β [53] and increased proportion of circulating T-regulatory cells [54]. This “immunosuppressive phase” results in a heightened risk for secondary bacterial infections [51, 55]. We will explore whether severe HIV-TB, through similar mechanisms, results in an immunosuppressive state (prior to ART) that exacerbates HIV-related immunosuppression and may predispose to bacterial infections. Specifically, we will explore whether severe HIV-TB and mortality are associated with:

- i) Immune activation-induced apoptosis;
- ii) Increased programmed death-1 (PD-1) signaling;
- iii) Anti-inflammatory cytokine profile.

Experiments will be performed on samples from:

- 290 patients in the cohort sampled consecutively provided FACS can be performed the same day (estimated mortality of 15% will result in 44 fatal cases and 246 survivors);
- Non-TB control group (n=30).

i) Immune-activation induced apoptosis

We hypothesise that severe HIV-TB induces apoptosis of immune cells and that this is associated with mortality. PBMC will be separated and same day FACS analysis for surface markers of cell activation (CD38, HLA-DR) and a marker of apoptosis (Annexin-V) on CD4 and CD8 T-lymphocytes and monocytes will be performed on a BD LSR Fortessa instrument at the IDM. Data will be analysed using FlowJo software (TreeStar Inc, FlowJo Africa scheme).

ii) PD-1 signaling pathway

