Ligation of PD-1 (found on T and B cells and innate immune cells) by its ligands PD-L1 and PD-L2, results in cell cycle arrest, impaired proliferation and function, apoptosis and up-regulation of anti-inflammatory signals [56, 57]. In septic shock patients, PD-1, PD-L1 and PD-L2 expression on monocytes and CD4 T-lymphocytes was significantly elevated. Furthermore, PD-L1 expression on monocytes was higher in those patients with septic shock that died, and higher PD-1 expression on monocytes was associated with secondary nosocomial infections [56]. Other studies demonstrated upregulation of PD-1 on T cells and PD-L1 on monocytes in septic shock patients [58] and that PD-1 upregulation leads to macrophage dysfunction in sepsis [59]. Murine models have demonstrated improved survival from sepsis when the PD-1/PD-L1 pathway is blocked [58, 59]. Using FACS on fresh PBMC (as above), we will assess

expression of PD-1 and its ligands on T cells (CD4 and CD8), monocytes and neutrophils.

iii) Anti-inflammatory cytokines and ratio to pro-inflammatory cytokines

Lower TNF- α responses to LPS and heat-killed *M.tuberculosis* were associated with poor outcome in Malawi [60]. In Zambia fatal TB was associated with reduced LPS-induced TNF- α , IL-6 and IL-8 [61]. In sepsis higher IL-10 concentrations have been linked to mortality [62, 63].

We hypothesise that fatal HIV-TB is associated with higher concentrations of anti-inflammatory cytokines and higher ratio of anti-inflammatory to pro-inflammatory cytokines. Cytokine concentrations will be measured using Luminex (Bio-Plex platform) and ELISA in stored plasma. A 12-plex Luminex assay will be run: IL1-beta, IL-1 receptor antagonist, IL-4, IL-5, IL-6, IL-8, IL-10, IL-12, IL-13, IFN- γ , TNF- α , GM-CSF. TGF- β will be assayed using ELISA. Ratios of anti-inflammatory to pro-inflammatory cytokines will be derived (eg. IL-10/IFN- γ).

The findings from these 3 experiments will be analysed comparing survivors vs fatal cases vs non-TB controls. Data will also be correlated with measures of *M.tuberculosis* load, LPS, HIV viral load and CMV viral load in univariate analysis and multiple linear regression models.

1e) Paradoxical TB-associated immune reconstitution inflammatory syndrome (TB-IRIS)

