660 patients will be enrolled. Assuming 5% loss to follow up, 630 patients will complete the study. We will exclude from major analyses patients diagnosed with rifampicin resistance (estimated 5% [77], n=30), leaving 600 for analysis. This will allow us to detect statistical significance for a two-fold difference in urinary LAM, a 15% difference in plasma LPS and a difference in the percentage of patients with detectable CMV viraemia of 20% in survivors and 40% in those with fatal outcome (or 10% and 30% respectively).

Sample size for FACS experiments (44 fatal cases vs 246 survivors) was based on Annexin-V experiments, allowing us to detect a significant difference in the proportion of CD4 T-lymphocytes that are Annexin-V+ of 5% in survivors and 20% in those who die (alpha=0.05, beta=0.2).

Characteristics of the study population:

Number of participants:

660 participants with HIV-TB co-infection.

Inclusion criteria:

1. Microbiological diagnosis of TB, or clinical diagnosis that fulfills WHO criteria for smear-negative or extrapulmonary TB [78] or suspected to have active TB based on clinical presentation
2. 18 years or older
3. Informed consent from patient (unless drowsy/confused – see below)
4. HIV seropositive
5. CD4 count \leq 350cells/ μ l

Exclusion criteria:

1. HIV seronegative or testing declined
2. Pregnant
3. 3 or more doses of TB treatment received during the admission or has been on TB treatment within one month of admission

TB case definitions:

TB will be investigated with 2 sputa for Xpert MTB/RIF and TB culture, Myco/F Lytic blood culture, urinary lipoarabinomannan (LAM) and samples from appropriate extrapulmonary sites for TB culture. Chest radiographs will be performed in all and abdominal ultrasound at clinician discretion. We will stratify analyses according to:

- 1) Confirmed TB: Microbiologically proven TB (by culture or Xpert MTB/RIF, or post-mortem findings of AFB+ or culture+) (predicted to be > 70% based on previous study at our hospital [79])
- 2) Probable TB: TB not confirmed, but urinary LAM+ or fulfill WHO criteria [78] unless an alternate diagnosis is made during follow-up or post-mortem.

Vulnerability:

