Relatives will be approached for permission for post-mortem examinations. If unwilling to have a full post-mortem performed, permission will be sought to undertake post-mortem needle biopsies of lung, liver and spleen and bone marrow – an approach that yields important diagnostic information in HIV-infected patients [14, 81]. Tests performed on tissue samples will include: histological stains; Gram, fungal and ZN stains; immunohistochemical staining (CMV); and bacterial, TB and fungal cultures. This study will be performed in collaboration with [name] (Anatomical Pathology, UCT).

Study Outline of Activities:

	D0	D3	Wk2	Wk4	Wk8	Wk12	Deterioration
Informed consent	x						
Clinical Assessment	x	x				x	x
Samples Collected	x	* PK					#x
^Δ ART initiation CD4 ≤ 50			x				
^Δ ART initiation CD4 >50			x				

D: Day

Wk: Week

ART: Antiretroviral Therapy

PK: PK substudy in a subset of participants

* PK samples will be stored and run in batches retrospectively.

Samples taken at time of deterioration will not be research samples, but standard of care samples appropriate to investigate the patients' condition at that time point.

^Δ If patient is not on ART at time of recruitment

Detailed Study Procedures:

Study procedure	Time Point	Detail	Volume	Standard of care or research
Clinical Assessment	All time points	Examine for features of sepsis syndrome and TB IRIS	NA	Standard of care
	D0	* Pan ophthalmic fundoscopy for features of CMV retinitis	NA	Research
Echocardiography	D0 & Deterioration	* Assess left ventricular function	NA	Research
Blood tests	D0 & Deterioration	Chemistry: * Glucose	2 ml	Standard of care
		* Lactate		Research
		* D-dimer	5 ml	Research
		* Pro-calcitonin	1 ml	Research
		* Venous blood gas	1 ml	Research
		* Liver function tests	5 ml	Standard of care
		* Renal function tests		Standard of care
		* CRP		Standard of care
		Haematology: * Full blood count and differential	4 ml	Standard of care
		Plasma: LPS concentration	2 ml	Research
		Soluble CD14	1 ml	Research
		Intestinal fatty acid binding protein	1 ml	Research
		Microbiology: * Bacterial blood culture	8 ml	Standard of care
		* Mycobacterial blood culture	5 ml	Research
		* Serum cryptococcal antigen lateral flow assay	0.5 ml	Research
		Virology: CMV viral load	2 ml	Research
		* HIV viral load	2 ml	Research
		Immunology: PBMC	10 ml	Research
		* CD 4 count	2 ml	Standard of care
		Genetic: DNA	2 ml	Research
Luminex and ELISA for cytokines	Plasma from PBMC sample	Research		

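### Neutrophil PD-1, PD-L1 and PD-L2 expression is planned on separated PBMC, a preparation that does not represent circulating neutrophils (minor, confined to experiment 1d ii)

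*Protocol*

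**What the plan says.** Protocol section 1d describes three laboratory experiments on a consecutive subset of 290 cohort patients, provided flow cytometry can be done the same day, and 30 non-TB controls.

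- **Experiment i (apoptosis)** fixes the preparation: "PBMC will be separated and same day FACS analysis for surface markers of cell activation". The markers are read "on CD4 and CD8 T-lymphocytes and monocytes will be performed on a BD LSR Fortessa instrument".
- **Experiment ii (PD-1 pathway)** refers back to that preparation: "Using FACS on fresh PBMC (as above), we will assess". The sentence then lists what will be assessed: "expression of PD-1 and its ligands on T cells (CD4 and CD8), monocytes and neutrophils".
- **The Detailed Study Procedures table** has one blood line that could serve these assays, "Immunology: PBMC", at 10 ml. The only other immunology line is a CD4 count. Cytokine plasma is taken from the PBMC sample.
- **The closing paragraph of section 1d** commits the results of the three experiments to comparison of survivors, fatal cases and non-TB controls. It also commits them to correlation and regression against *M. tuberculosis* load, LPS, HIV viral load and CMV viral load.

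**The concern.** PBMC stands for peripheral blood mononuclear cells, that is, lymphocytes and monocytes. Neutrophils are polymorphonuclear and are separated off when PBMC are isolated. Experiment i is consistent with this, since every cell type it reads is mononuclear. Experiment ii keeps the same preparation and adds a cell type that the preparation excludes.

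A laboratory that followed the text literally would have few or no neutrophil events, or would gate on whatever granulocytes remain in the PBMC layer. In the second case the results would be reported as neutrophil PD-1 expression and carried into the survivor, fatal-case and control comparisons, although they describe a residue of the separation. The assay is run on fresh cells on the day of sampling. The specimens listed for storage are plasma, serum, urine, PBMC and DNA, none of which could supply neutrophils later. The method therefore has to be right when sampling starts.

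**Working it through.** **1. The plan's own figure.** The only sample size attached to the flow cytometry work is 44 fatal cases versus 246 survivors, stated under sample size calculations and in section 1d ("estimated mortality of 15% will result in 44 fatal cases and 246 survivors"). Split: 290 × 0.15 = 43.5 and 290 × 0.85 = 246.5, which agrees with 44 and 246.

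Inputs from the sample size section: 20% of CD4 T-lymphocytes Annexin-V-positive in those who die, 5% in survivors, alpha 0.05, beta 0.2. The protocol does not state sidedness; I assume two-sided. Allocation ratio from the plan's split: k = 246/44 = 5.591.

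- Pooled proportion: (0.20 + 5.591 × 0.05)/(1 + 5.591) = 0.0728.
- Fatal cases, no continuity correction: n = [1.96·√((1 + 1/k) × 0.0728 × 0.9272) + 0.842·√(0.20 × 0.80 + 0.05 × 0.95/k)]² / 0.15² = [0.553 + 0.345]² / 0.0225 ≈ 35.9, so 36 fatal cases and about 201 survivors, 237 in total.
- With continuity correction: (n/4)·[1 + √(1 + 2(k + 1)/(n·k·0.15))]² = (35.9/4) × (1 + 1.199)² ≈ 43.4, so 44 fatal cases and 44 × 5.591 = 246 survivors, 290 in total.

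The stated size reproduces with the continuity-corrected formula. Without the correction, power at 44 versus 246 is about 0.86. All of this rests on Annexin-V in CD4 T-lymphocytes, so the neutrophil readout does not enter it.

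**2. The statements side by side.**

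| Place in protocol | Preparation | Cells read |
|---|---|---|
| 1d i | Separated PBMC, same day | CD4 and CD8 T cells, monocytes |
| 1d ii | Fresh PBMC, same as 1d i | CD4 and CD8 T cells, monocytes, neutrophils |
| Detailed Study Procedures | 10 ml labelled PBMC | not stated |

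The neutrophil entry in 1d ii is the only one that does not fit its preparation.

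**3. Search for another source of neutrophils.** The other blood lines in the procedures table are assigned to other tests: full blood count and differential, CD4 count, DNA, and PLEX-ID for bacterial DNA, besides chemistry, plasma assays, cultures and viral loads. No section or table line mentions whole-blood staining, a lysed-blood preparation or a granulocyte fraction.

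**4. Scope.** Section 1d ii names one receptor and two ligands, so three markers. Over four cell populations that is 3 × 4 = 12 marker-by-cell readouts, of which 3 are affected. Samples: 290 + 30 = 320 at most.

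**The case against.** The strongest reply is that this is a slip in one list, in a sub-aim that the protocol presents as exploratory. The literature cited for the PD-1 experiment concerns monocytes, T cells and macrophages, and none of the three questions listed in section 1d names neutrophils. The study timeline sets aside months 1 to 6 for preparing SOPs, where bench preparation is normally settled. A laboratory would probably notice that neutrophils were missing. The label on the 10 ml tube also proves little: the same tube yields cytokine plasma, so it is not reserved for mononuclear cells, and an aliquot taken before separation would not need its own table line.

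Most of this stands, and it limits the weight of the point. It does not remove it: the text does not merely leave the preparation open, it names one that excludes the cell type.

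Three stronger readings are tempting and are not supported:

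- *Impaired neutrophil function is a study hypothesis.* The phrase "monocyte deactivation, impaired neutrophil function, lymphocyte dysfunction and apoptosis" occurs in background text on bacterial sepsis. The study's own questions are activation-induced apoptosis, PD-1 signaling and cytokine profile.
- *The residual granulocytes track severity of illness and would create a false difference between fatal cases and survivors.* Nothing in the protocol gives or implies such a relation, so no direction of bias can be claimed.
- *The readout cannot be obtained from the blood collected.* The blood drawn suffices; only the named preparation is wrong. Nor are the 320 samples lost, since they still serve the T-cell and monocyte readouts.

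**Conclusion.** The point holds as a contained inconsistency between a planned readout and its stated preparation. Followed as written, PD-1, PD-L1 and PD-L2 on neutrophils cannot validly represent circulating neutrophils in any of the up to 320 samples (290 cohort, 30 controls). The other nine marker-by-cell readouts of experiment 1d ii, all of experiment 1d i, the 44 versus 246 sample size and the 12-week mortality outcome are untouched. I rate it minor.

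The conclusion assumes that PBMC carries its ordinary meaning, which the protocol does not spell out, and that no unstated whole-blood step exists. If the laboratory already stains whole blood before separation, only the wording needs correcting.

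**What to change.** Preferred: before PBMC separation, set aside a small aliquot of the existing 10 ml immunology tube, stain it the same day as lysed whole blood, and gate neutrophils there. Keep PBMC for T cells and monocytes. State this in section 1d ii and beside the PBMC line in the procedures table. No further blood is drawn, so neither the total of about 55 ml nor the 30 ml limit for symptomatic anaemia changes. The cost is one extra stain and acquisition per sample, up to 320. This is a real though small load, because inclusion in this subset already depends on same-day flow cytometry.

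Alternative: delete neutrophils from the list of cells in section 1d ii. This costs only a wording change and gives up the neutrophil readout. In either case, granulocytes remaining in the PBMC layer should not be analysed as neutrophils.

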1b) Is fatal HIV-TB associated with translocation of bacteria and their products from the intestine into blood?

Under this aim, the first hypothesis is that in patients with severe HIV-TB, intestinal translocation of bacterial products (LPS and bacterial DNA) will be higher than in control HIV-infected patients with similar CD4 counts who do not have TB. The second hypothesis is that mortality will be associated with higher levels of bacterial product translocation. Thirdly we hypothesise that translocation of viable intestinal bacteria in some patients results in life-threatening deterioration and death.

To test the first 2 hypotheses the following will be performed:

- i) Plasma LPS concentration using Chromogenic Limulus Amebocyte Lysate test [17];
- ii) Plasma soluble CD14 (secreted by macrophages/monocytes in response to LPS) by ELISA [17, 34];

- iii) Plasma intestinal fatty acid binding protein (I-FABP; a marker of small intestine mucosal damage) [35-38] by ELISA;
- iv) Whole blood bacterial DNA concentrations will be measured using Abbott PLEX-ID platform [39-41]. Specimens will be shipped to Abbott Laboratory (Carlsbad, CA, US). Steps are: DNA extraction (using reagents prepared to minimise bacterial contamination), PCR amplification of bacterial DNA using broad-range, unbiased primers targeted at conserved regions of bacterial genomes, then electrospray ionization/mass spectroscopy. Amplicons are identified by ESI/MS based on recognisable patterns of base composition for different bacterial species. Quantification is performed by comparison with an internal calibrant. Similar approaches were used to study translocation in liver disease [15, 16] and inflammatory bowel disease [42].

We will perform LPS, sCD14 and I-FABP in all 660 participants and compare with the non-TB control group (n=90). For the PLEX-ID we will perform 270 PLEX-ID assays in a nested case-control study (90 fatal cases, 90 survivors and 90 non-TB controls). For all experiments comparisons will be made between fatal cases and survivors using multiple linear regression to adjust for covariates (eg. CD4 count, antibiotic treatment).

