20 patients will be enrolled monthly. When potential enrollees exceed capacity on a day then recruitment will be randomised (using simple random allocation calculator) to avoid bias. This method of selecting participants to enroll will be described in an SOP. The study counselor or study nurse will administer the informed consent document with support from the study medical officer. The informed consent document makes it clear that patients will receive the same standard of care should they decline to take part in the study and that collection and testing of genetic material is optional. In addition, they will be specifically requested to consent to storage of samples for future research and informed that this is optional. After informed consent is obtained, the study team will follow up patients for 12 weeks initially as an inpatient then as an outpatient.

Research procedures and follow up (see table below):

Cumulative mortality at 12 weeks will be ascertained. Paradoxical TB-IRIS and other causes for clinical deterioration will be ascertained during the 12 weeks. Participants not on ART will initiate ART 2-8 weeks into TB treatment (2 weeks if $CD4 \leq 50/\mu l$).

Study assessments will be at 3 days (while in hospital) and subsequently every 3 days while patient remains hospitalized. The study team will review patients at any re-hospitalisation. The team will make telephonic contact at 4 weeks after enrolment and will do a clinical review of all participants at 12 weeks after enrolment. Additional study visits will be arranged in order to determine the cause of and assist with management of clinical deterioration if necessary. We will investigate for TB drug resistance and additional diagnoses (including serum cryptococcal antigen testing [80]). Patients with drug resistance or other diagnoses will be included in the study, with these findings recorded.

At discharge from hospital patients will be referred to their local TB clinic and for continuation of their TB treatment and their local ART clinic for initiation or continuation of ART. A referral letter will be written by the KDH staff or the research staff. If at any time point there is concern that patients are not on appropriate medication, the team will contact their local clinic. They will be asked to bring their medications and TB card to the clinical review visit.

Post-mortem examinations:

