Data quality control and assurance measures will be put in place. These will include having all clinical data capture forms being checked and signed off by one other member of the study team. Data entered on the study database will be entered by one data capturer, but will be checked by a member of the study team or by another data capturer. Any errors will be recorded and discussed at the monthly study meeting. Upon completion of the study we will ensure that 3 copies of the raw data are backed-up for long term storage: one on a UCT server, one on a remote server and one on an external hard-drive that the applicant will keep secure. These data capture, entry, management and access systems have been developed in the course of many TB-HIV and other HIV studies that we have undertaken to date.

Data analysis:

TB suspects who do not have active TB (after full clinical investigation has been completed and all results obtained) will not be included in the analysis of primary endpoints. Their data may be used in secondary analyses or as control subjects. Univariate analysis will compare those who survive 12 weeks to those with fatal outcome. Bonferroni correction for multiple comparisons will be performed where appropriate. Multivariable logistic regression modeling will be approached based on pre-specified hypotheses, articulated where possible through directed acyclic graphs. Demographic variables, CD4 count, viral load, antibiotic treatment will be explored as potential confounders in addition to hypothesis specific variables. Comparison with non-TB control patients will be performed for several of the experiments as described. Data will be analyzed using de-identified study numbers.

Description of risks and benefits:

Potential risks and discomforts: This is an observational trial and there are no study specific interventions. Collection of study samples by means of phlebotomy carries minimal risk of bruising, infection at the collection site and bleeding after phlebotomy. Phlebotomy may be uncomfortable or painful during the procedure, but this resolves as soon as the procedure has been completed. The total volume of blood drawn is ~ 55ml. This amount of blood drawn would not cause complications unless patients are severely anaemic.

Risk classification: The study as a whole carries minimal risk for participants and harm due to study participation is not anticipated.

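### The 600 patients for analysis are an upper figure: the attrition chain has no deduction for enrolled TB suspects in whom TB is later ruled out

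*Protocol*

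**What the plan says.** **Attrition chain (Protocol, Sample size calculations).** The chain begins "660 patients will be enrolled". It continues "Assuming 5% loss to follow up, 630 patients will complete the study", and ends "We will exclude from major analyses patients diagnosed with rifampicin resistance (estimated 5% [77], n=30), leaving 600 for analysis". On that basis the section claims to detect a two-fold difference in urinary LAM, a 15% difference in plasma LPS, and CMV viraemia of 20% against 40% (or 10% against 30%).

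**Eligibility (Inclusion criteria, item 1).** Besides microbiological and WHO-criteria diagnoses, a patient qualifies if "suspected to have active TB based on clinical presentation".

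**Analysis rule (Data analysis).** The rule reads "TB suspects who do not have active TB (after full clinical investigation has been completed and all results obtained) will not be included", and it applies to the primary endpoint analysis. The next sentence allows their data in secondary analyses or as controls.

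**Comparison with controls (question 1b).** "We will perform LPS, sCD14 and I-FABP in all 660 participants and compare with the non-TB control group (n=90".

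**TB case definitions.** Analyses are stratified into Confirmed TB (predicted to be more than 70%) and Probable TB. A patient given another diagnosis during follow-up or at post-mortem cannot be Probable TB.

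**The concern.** The eligibility rule and the analysis rule together create a third exclusion: patients enrolled as suspects who turn out not to have TB. The chain has no term for them, and the protocol nowhere says that they are replaced or that enrolment continues until 660 true cases are reached. If any such patients occur, fewer than 600 remain.

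The claim at stake is the 15% LPS difference. It needs 536 patients by the protocol's own table, the largest requirement among the claims made, so it has the least reserve.

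Question 1b raises a related problem of definition. Taken literally, it puts every enrolled participant on the TB side of a comparison with non-TB controls, whereas the Data analysis section allows ruled-out suspects to serve on the control side. The two places do not agree on where these patients belong.

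**Working it through.** **1. The stated chain.** 660 × 0.95 = 627, stated as 630. 5% of 630 = 31.5, stated as 30. 630 − 30 = 600. Unrounded, 660 × 0.95 × 0.95 = 595.65. The chain is right for the two losses it names.

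**2. The stated LPS sample size.** Inputs from the LPS table: means 128 and 147 pg/ml, SD 56, alpha 0.05 (taken as two-sided), power 80%. Mortality of 15% gives 15:85 groups.

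- Survivors: (1 + 0.85/0.15) × ((1.960 + 0.842) × 56/19)² = 6.667 × 68.2, rounded up to 455.
- Deaths: 455 × 0.15/0.85, rounded up to 81.
- Total 536, as stated. The same formula reproduces the two-fold LAM figure: 205 + 37 = 242.

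**3. Adding the missing term.** Let f be the share of enrolled patients in whom TB is ruled out. The protocol gives no value, so the values below are assumptions. The 15% mortality is assumed to hold among those who remain.

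- N = 600 × (1 − f)
- SE = 56 × √(1/(0.85N) + 1/(0.15N)) = 56 × √(7.843/N)
- Power = Φ(19/SE − 1.96)
- Difference detectable with 80% power = 2.80 × SE, as a percentage of 128

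At N = 600: SE = 6.40, 19/6.40 = 2.97, power = Φ(1.01) = 0.84. At N = 480: SE = 7.16, 19/7.16 = 2.65, power = Φ(0.69) = 0.76.

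| Assumed f | N | Expected deaths | Power, 128 v 147 | Detectable LPS difference |
|---|---|---|---|---|
| 0 (as stated) | 600 | 90 | 0.84 | 14.0% |
| 5% | 570 | 85.5 | 0.82 | 14.4% |
| 10% | 540 | 81 | 0.80 | 14.8% |
| 15% | 510 | 76.5 | 0.78 | 15.2% |
| 20% | 480 | 72 | 0.76 | 15.7% |

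**4. Where the LPS claim fails.** 1 − 536/600 = 64/600 = 10.7%. From the unrounded 595.65 it is 1 − 536/595.65 = 10.0%. The table's row is really 19/128 = 14.8%. A difference of exactly 15% (19.2 pg/ml) needs 525, which moves the threshold to 1 − 525/600 = 12.5%.

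**5. The other claims.** They need 242 (LAM), 334 (CMV 20% v 40%) and 246 (CMV 10% v 30%). All lie well below 480. The most demanding of them, 334, is lost only if f exceeds 1 − 334/600 = 44%.

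**6. Question 1b.** If a share f of the TB side has no TB, and if their LPS resembles that of the controls (an assumption), the TB-side mean is (1 − f) × TB mean + f × control mean. The expected difference from controls is then (1 − f) times its true size: 90% of it at f = 10%, and 80% at f = 20%.

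**The case against.** - **The subtraction is correct.** This stands. What is missing is an assumption, not a sum.
- **660 may already mean true cases.** Study design and Number of participants both describe the 660 as HIV-TB patients, so suspects might be enrolled on top. This is possible, but the chain counts patients enrolled and no such rule is written. It is an ambiguity that the protocol should settle.
- **The effect may be small.** Unconfirmed patients can remain as Probable TB, and the capacity-to-consent section describes eligible patients as about to start TB treatment, which suggests that few are loosely suspected. The reserve of 64 patients over 536 absorbs a small f. This stands, and it limits the weight of the point.
- **The 1b sentence concerns which assays are run.** The 1b hypothesis is about patients with HIV-TB, and a ruled-out suspect fits neither TB stratum. This also stands in part. A reader might infer that non-TB patients will certainly be analysed as TB cases, but the documents show only that the wording of 1b conflicts with the option to use them as controls.

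Two other stronger inferences are not supported:

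- **That ruled-out patients cannot be replaced in time.** With "20 patients will be enrolled monthly", 660 takes 33 months. But Study site gives about 50 eligible admissions a month, and 36 months (months 7 to 42) at 20 a month is 720, enough for f up to 1 − 660/720 = 8%. The timeline table as read here does not show where recruitment ends.
- **That up to 30% will be ruled out, because more than 70% are predicted to be confirmed.** Unconfirmed is not ruled out, so that figure neither gives nor bounds f.

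**Conclusion.** The concern holds as an omitted assumption. The protocol creates an exclusion that its attrition chain does not count, so 600 is the most that can be analysed from 660 enrolled, and any non-zero ruled-out share without replacement gives fewer.

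The consequence is modest and falls on one claim. Over an assumed f of 5% to 20%, power for the LPS difference goes from 0.82 to 0.76, crossing 80% at about 10.7%. The LAM and CMV claims are not threatened. These figures rest on the protocol's own means, SD and 15% mortality; only f is supplied from outside, and the documents offer no basis for choosing a value.

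For 1b, the finding is that two sections need reconciling. A reader might wish to attach a power loss to the TB-versus-control comparison. The documents do not allow it: they give no expected TB-versus-control difference (the 19 pg/ml is between fatal cases and survivors) and nothing about LPS in ruled-out suspects. Only the proportional shrinkage to (1 − f) can be stated, and that is conditional on their resembling controls.

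**What to change.** 1. In Sample size calculations, add a line for suspects in whom TB is ruled out, giving the assumed share and a range. Restate the analysable number and the LPS difference it detects: about 14.8% to 15.7% for f of 10% to 20%.
2. Alternatively, state that 660 counts only confirmed and probable TB, with suspects enrolled in addition. Total enrolment would then be 660/(1 − f): 695, 734, 777 or 825 for f of 5%, 10%, 15% or 20%.
3. In 1b, define the TB side of the comparison with controls as all Confirmed and Probable TB participants, and make this agree with the Data analysis section on whether ruled-out suspects may join the control group.

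Items 1 and 3 are changes of wording, and the cost is a slightly less favourable LPS figure. Item 2 costs extra enrolment and, at the larger shares, recruitment time.
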